### **3.5 Study-wide Stopping Rules**

If after 20 patients have been accrued to the study, 30% or more are unable to stay on acalabrutinib due to AEs, enrollment will be stopped, and a comprehensive review of safety will be performed by the study chair, primary investigators, and representatives of Acerta Pharma/AstraZeneca.

## **4. STUDY REGISTRATION**

The patient must willingly consent to participate after being informed of the procedures to be followed, the experimental nature of the treatment, potential benefits, treatment alternatives, side-effects, risks, and discomforts. Institutional Review Board (IRB) approval of this protocol

and any associated ICFs are required. Eligible patients who wish to participate in the study will be enrolled into the study.

Registration must occur prior to the initiation of protocol therapy. Patients eligible to participate in the study may be enrolled by each site following the patient registration instructions provided by the Sarah Cannon Development Innovations (Innovations) study contact. Patient registration follow-up and/or confirmation will be provided via email within approximately 24 hours or by the next business day.

[figure not shown]
## 5. STUDY DESIGN

This is a single arm, multi-center, Phase II study of subjects with MCL who will receive acalabrutinib as maintenance therapy post-BMT. In general, subjects will provide informed consent prior to BMT to collect the required central labs. However, a limited number of subjects may be allowed to provide informed consent following BMT, determined on a case-by-case basis by the Principal Investigator (PI). In this event, any of the study assessments required prior to BMT not performed for standard of care will not be required.

Subjects will undergo a standard of care BMT with conditioning regimen determined by the treating physician per institutional guidelines. The BMT is not considered part of this study. Following completion of the BMT, a second screening will begin between Day 80 and Day 100. Maintenance therapy with acalabrutinib will begin on Day 100 in 28-day cycles. Subjects will self-administer 129 mg acalabrutinib BID until they reach 2 years post-BMT (approximately 22 cycles). Subjects who experience PD while on study will be encouraged to provide a fresh biopsy to assess lymphoma genome alterations. All subjects will be followed for up to 5 years post-BMT for PFS.

Approximately 50 subjects are planned to be enrolled after receiving BMT.

## Figure 1 Study Schema

Subjects will self-administer acalabrutinib 129 mg BID on a 28-day cycle.

Abbreviations: BM, bone marrow; BMT, blood or marrow transplant; MRD, minimal residual disease; SOC, standard-of-care.

## 5.1 Treatment Plan

In this clinical trial, the study drug only refers to acalabrutinib. The BMT is a non-investigational medicinal product and is not the study drug.

Acalabrutinib 129 mg will be self-administered orally BID on a 28-day schedule, with or without food, until the patient has reached approximately 2 years post-BMT.

Acalabrutinib will be administered until PD, unacceptable toxicity, or the subject discontinues treatment for any other reason.

## 5.2 Concomitant Medications

Patients will be instructed not to take any additional medications during the course of the study without prior consultation with the research team. At each visit, the patient will be asked about any new medications he/she is taking or has taken after the start of the study drug.

### 5.2.1 Permitted Concomitant Medications

Standard post-BMT therapy is permitted and encouraged. Prophylaxes for *pneumocystis jirovecii* pneumonia (PJP) and herpes simplex/varicella zoster viruses (HSV/VZU) are recommended for 6 months and 1 year, respectively. Antiemetics are permitted if clinically indicated. Supportive medications in accordance with standard practice are permitted (such as for emesis, diarrhea, and nausea [Appendix H]).

Use of granulocyte growth factors (filgrastim and pegfilgrastim) or red blood cell growth factors (erythropoietin) are permitted per institutional policy and in accordance with the American Society of Clinical Oncology (ASCO) guidelines (Smith et al 2006, Smith et al 2015). Blood and platelet transfusions may be given in accordance with institutional policy.

**For subjects at risk for infectious pneumonitis based on prior history or comorbid conditions:**

Infection control should be considered for select subjects (e.g., those with a history of recurrent pneumonias). Initiation of antibiotic prophylaxis against pneumocystis infection (e.g., with trimethoprim-sulfamethoxazole, dapsone, aerosolized pentamidine, or atovaquone) beginning before study drug administration may be warranted. Such support may also offer the benefit of

reducing the risk for other bacterial infections (Stern et al 2014). Prophylaxis with intravenous immunoglobulins (IVIG) may be appropriate in subjects with low immunoglobulin levels (Raanani et al 2009). Local practices or guidelines regarding infection prophylaxis may be followed.

#### **For infections:**

Bacterial/viral/fungal prophylaxis is allowed per institutional standards (see Appendix H).

#### **5.2.2 Prohibited or Restricted Concomitant Medications**

The following treatments are prohibited during the treatment period of the study:

- Any chemotherapy, anticancer immunotherapy, experimental therapy, radiotherapy, warfarin or equivalent vitamin K antagonists (e.g., phenprocoumon), or corticosteroids (at dosages equivalent to prednisone >20 mg/day for longer than 2 weeks) are prohibited.
- The concomitant use of strong inhibitors/inducers of CYP3A4 (Appendix G) should be avoided when possible (Section 5.3). If a subject requires a strong CYP3A inhibitor while on study, monitor the subject closely for potential toxicities. For additional information on drugs with potential drug-drug interactions, refer to Section 5.3.
- At study entry, subjects may be using topical or inhaled corticosteroids or low-dose steroids ( $\leq 10$  mg of prednisone or equivalent per day) as therapy for comorbid conditions, but use of corticosteroids as therapy for the lymphoid cancer, other than palliative, is not permitted. During study participation, subjects may also receive corticosteroids at any required dosage as needed for treatment-emergent adverse events (TEAEs).

#### **5.3 Drug-Drug Interactions**

At the systemic exposure levels expected in this study, acalabrutinib inhibition of CYP metabolism is not anticipated.

However, acalabrutinib is metabolized by CYP3A. Concomitant administration of acalabrutinib with a strong CYP3A and P-glycoprotein (P-gp) inhibitor, itraconazole increases exposure by approximately 5-fold. Conversely, concomitant administration of acalabrutinib with a strong CYP3A inducer, rifampin, decreases acalabrutinib exposure and could reduce efficacy.

Consequently, the concomitant use of strong inhibitors/inducers of CYP3A (Appendix G) should be avoided when possible.

If medically justified, subjects may be enrolled if such inhibitors or inducers can be discontinued or alternative drugs that do not affect these enzymes can be substituted within 7 days before first dose of study drug. If a subject requires a strong CYP3A4 inhibitor or inducer while on study, monitor the subject closely for potential drug-related toxicities.

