#### **1.4.2 Pharmacokinetics and Pharmacodynamics of Acalabrutinib**

Acalabrutinib has a short pharmacokinetic (PK) half-life with a long-lasting pharmacodynamic (PDc) effect due to covalent binding to BTK. In a first-in-human (FIH) study in healthy subjects, acalabrutinib plasma time to maximum concentration (Tmax) values were between 0.5 and 1.0 hour for all dose cohorts (2.5 mg twice daily [BID] to 100 mg once daily [QD]), and mean half-life ranged from 0.97 hours to 2.1 hours. Acalabrutinib has an absolute oral bioavailability of 25%, is best taken with water, can be taken with or without food, and does not accumulate in plasma upon repeat-dose administration. Based on population PK analysis, acalabrutinib PK was linear over the 75 to 250 mg dose range. Variability in exposure to acalabrutinib is mainly due to a combination of gastric pH-dependent absorption and predominantly cytochrome P450 (CYP)3A mediated metabolism.

Acalabrutinib is extensively and almost completely metabolized. The most abundant circulating metabolite in humans was ACP-5862, which was formed by CYP3A-mediated oxidation and accounted for more than 10% of total acalabrutinib-related material. Within the Tec family of kinases, activities of acalabrutinib and ACP-5862 were quite similar.

ACP-5862 plasma area under the plasma-concentration time curve (AUC) was approximately 2- to 3-fold the AUC of acalabrutinib in healthy subjects, with a median half-life of 6.9 hours. Based on plasma profiling of radioactive metabolites, ACP-5862 exposure was higher in rats at a no observable adverse effect level (NOAEL) dose than in human subjects at a 100 mg dose. Excretion of [C] acalabrutinib-related radioactivity was essentially complete by 48 to 96 hours post-dose, with predominantly biliary-fecal excretion in rats, dogs, and humans.

Co-administration of acalabrutinib with strong inhibitors and strong inducers of CYP3A should be avoided; however, coadministration with grapefruit juice did not increase acalabrutinib exposure in healthy subjects. Therapeutic and supratherapeutic plasma acalabrutinib concentrations did not prolong the corrected QT (QTc) interval in a thorough QT study.

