### **3.3 Exclusion Criteria**

Patients who meet any of the following criteria will be excluded from study entry:

1. Subjects who have relapsed or progressed at any time prior to BMT
2. Subjects with known mutations that confer resistance to a BTK inhibitor.
3. Confirmed clinical PD since the time of BMT
4. Prior malignancy (or any other malignancy requiring active treatment), except for adequately treated basal cell or squamous cell skin cancer, in situ cervical cancer, or other cancer from which the subject has been disease free for  $\geq 2$  years or that will not limit survival to  $<2$  years. The exceptions are:
  - Subjects treated with curative intent  $>2$  years prior to enrollment and have a low probability of recurrence.

5. Clinically significant cardiovascular disease such as uncontrolled or symptomatic arrhythmias, congestive heart failure, or myocardial infarction within 6 months of screening, or any Class 3 or 4 cardiac disease as defined by the New York Heart Association Functional Classification (Appendix B).
6. Malabsorption syndrome, disease significantly affecting gastrointestinal function, resection of the stomach or small bowel that is likely to affect absorption, symptomatic inflammatory bowel disease, partial or complete bowel obstruction, or gastric restrictions and bariatric surgery, such as gastric bypass.
7. Known history of infection with human immunodeficiency virus (HIV) or any uncontrolled active systemic bacterial, fungal, parasitic or viral infection. Infections are considered controlled if appropriate therapy has been instituted and, at the time of screening, no signs of infection progression are present.
8. Known history of drug-specific hypersensitivity or anaphylaxis to study drug (including active product or excipient components).
9. Active bleeding or history of bleeding diathesis (e.g., hemophilia or von Willebrand disease).
10. Uncontrolled autoimmune hemolytic anemia or idiopathic thrombocytopenic purpura.
11. Requires treatment with a strong CYP3A4 inhibitor/inducer (Appendix G).
12. Requires or is receiving anticoagulation treatment with warfarin or equivalent vitamin K antagonists (e.g., phenprocoumon) within 7 days of first dose of study drug.
13. Prothrombin time (PT)/international normalized ratio (INR) or activated partial thromboplastin time (aPTT)  $>2 \times$  ULN (in the absence of lupus anticoagulant).

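### Once a strong CYP3A4 inhibitor or inducer is required on study, the only interaction-specific action is toxicity monitoring, and Appendix G neither grades inducers nor lists rifampin

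*Combined protocol and SAP*

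**What the plan says.** **Before treatment.** Section 1.4.2 states: "Co-administration of acalabrutinib with strong inhibitors and strong inducers of CYP3A should be avoided". Criterion 11 in Section 3.3 excludes a patient who "Requires treatment with a strong CYP3A4 inhibitor/inducer (Appendix G"). Section 5.3 lets a current user enrol only if the drug can be stopped or if "alternative drugs that do not affect these enzymes can be substituted within 7 days before first dose of study drug".

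**During treatment.** Section 5.2.2, in a list introduced as prohibited treatments, says: "The concomitant use of strong inhibitors/inducers of CYP3A4 (Appendix G) should be avoided when possible (Section 5.3"). It then adds, for inhibitors only: "If a subject requires a strong CYP3A inhibitor while on study, monitor the subject closely for potential toxicities". Section 5.3 gives the parallel instruction for both classes: "If a subject requires a strong CYP3A4 inhibitor or inducer while on study, monitor the subject closely for potential drug-related toxicities".

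**The risks named.** Section 5.3 says that "itraconazole increases exposure by approximately 5-fold", and that "a strong CYP3A inducer, rifampin, decreases acalabrutinib exposure and could reduce efficacy".

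**The drug list.** Appendix G grades inhibitors as strong, intermediate, weak or other possible. Its inducers form a single ungraded list.

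**The concern.** The plan treats these drugs as incompatible with the study at entry. Once treatment has begun, a required one may be added with no action specific to the interaction beyond watching for toxicity.

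For an inducer, the expected problem is too little drug. Watching for toxicity cannot detect that, and nothing else in the interaction text addresses it. The primary endpoint is PFS at 2 years post-BMT, so under-exposure bears on what the trial is meant to measure.

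For an inhibitor, toxicity is the right thing to watch for. However, the patient stays at full dose while exposure rises, and the dose rules of Section 8 act only after toxicity has appeared. Section 7.5.1 lists serious hemorrhage, infection and cytopenias among the known risks. Section 3.2 admits patients with platelets of 75,000/mm³ and ANC of 1,000/mm³.

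Both the entry rule and the on-study rule turn on the word strong. For inducers, Appendix G does not say which ones qualify.

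**Working it through.** **1. What covers a required drug after the first dose.**
- Section 5.2: the patient consults the team before taking a new medicine, and medication is reviewed at visits. It does not say what the team should then do.
- Sections 5.2.2 and 5.3: avoid where possible; if required, monitor for toxicity.
- Sections 8.1 to 8.3, Tables 1 to 3: withhold, reduce or stop for toxicity or an intolerable AE. Other dose delays are discussed with the PI. Co-medication is not a trigger.
- Section 8.1: the maximum dose is 129 mg BID, so the dose cannot be raised to offset an inducer.
- Section 3.4: stop for a condition needing treatment that the protocol does not permit. This does not clearly apply, because 5.2.2 and 5.3 provide for continuing with monitoring.

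Prevention and reaction to toxicity are therefore covered. What to do about acalabrutinib when the drug is unavoidable is not.

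**2. Inducers.** Section 5.3 names lower exposure and possible loss of efficacy; its instruction is to look for toxicity. The two do not match, and the 5.2.2 sentence leaves inducers out.

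**3. Appendix G.** The inducer list has 13 entries, none graded. Rifampin, the one inducer that 5.3 calls strong, is absent.

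**4. Inhibitors: what 5-fold could mean.** The 5-fold figure cannot be re-derived from the documents, and 5.3 does not say whether it covers parent drug only. Section 1.4.2 says the metabolite ACP-5862 is formed by CYP3A, has 2 to 3 times the parent AUC and has similar activity within the Tec kinases. Set parent exposure alone to 1.

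- *Reading A, 5-fold applies to total active exposure.* On BID: 5 times. On 129 mg QD, half the daily dose: 5/2 = 2.5 times.
- *Reading B, 5-fold is parent only, with equal potency (both assumptions).* Baseline = 1 + 2 = 3 to 1 + 3 = 4 units.
  - Metabolite formation fully blocked: 5/4 = 1.25 to 5/3 = 1.67 times.
  - Metabolite unchanged: (5 + 3)/4 = 2.00 to (5 + 2)/3 = 2.33 times.
  - On 129 mg QD: 1.25/2 = 0.63 to 2.33/2 = 1.17 times the intended daily exposure.

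The QD step might roughly restore intended exposure (B) or leave it at 2.5 times (A). The documents do not settle which, so QD cannot simply be written in as the answer.

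**5. Scale on the primary endpoint.** Section 10.2 plans on 45 patients and 80%, that is 36/45. The exact (Clopper-Pearson) 95% interval is 65.4% to 90.4%, matching the stated 65% to 90%. One more progression gives 35/45 = 77.8%, a shift of 80.0 − 77.8 = 2.2 points. This is a binomial approximation to the planned Kaplan-Meier estimate. How many such events would occur, if any, cannot be derived.

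**The case against.** Excluding known users at entry and handling unforeseen need by monitoring is an ordinary design choice, and much of the protection exists. Avoidance where possible already implies using an alternative. Section 5.2 requires consultation. Section 8 withholds for toxicity, including the cytopenias of most concern. Close monitoring goes beyond the scheduled visits, and 8.1 mentions weekly laboratory checks. Section 1.4.2 reports no QTc prolongation at supratherapeutic concentrations. Efficacy is followed by scans at 6, 12, 18 and 24 months and by serial MRD.

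Most of this stands, and it rules out several stronger readings that a reader might infer:

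- *That the plan has no rule at all to substitute, hold or stop.* It has general ones. The gap is the interaction-specific step once the drug is unavoidable.
- *That patients would have five times the active drug, with matching toxicity.* The 5-fold figure is for one inhibitor and may be parent only; the documents give no exposure-toxicity relation.
- *That lost efficacy would go unseen because no PK sample is scheduled.* Scans and MRD would pick up relapse, though only after the under-exposure had occurred.
- *That Section 5.2.1 licenses strong azole prophylaxis.* Its permission for fungal prophylaxis is general, and the 5.2.2 restriction is the specific rule. Because Appendix G grades four azoles strong (itraconazole, ketoconazole, posaconazole, voriconazole), a cross-reference is useful, but there is no outright contradiction.
- *That glucocorticoids on the inducer list make the steroid rule unworkable.* Section 5.2.2 regulates corticosteroids directly, and that rule governs.

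The objection does not answer the inducer sentence, which points at the wrong risk, or the ungraded list on which criterion 11 depends.

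**Conclusion.** The point holds as a moderate one, worth an amendment. The inducer instruction does not address the risk that Section 5.3 itself names. The inhibitor instruction allows full dose to continue until toxicity appears. Appendix G cannot support a rule about strong inducers.

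The only stated size is about 5-fold for itraconazole. In active exposure this is about 1.25 to 2.3 times if the figure is parent only and potencies are equal, or 5 times if it applies to total active exposure. The documents give no size for the inducer effect, no figure for other strong inhibitors and no expected number of users. It would therefore be wrong to infer that the 2-year PFS estimate is biased by any particular amount, or that the trial's validity is in doubt.

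**What to change.** - **(a) Sections 5.2.2 and 5.3:** state that a required strong inhibitor or inducer is first replaced by an agent that Appendix G does not grade strong (among azoles, fluconazole and isavuconazole are graded intermediate). For inducers this works only with (e).
- **(b) Strong inhibitor, no substitute:** interrupt acalabrutinib for a short course and restart at the prior dose. For prolonged need, decide with the Medical Monitor between 129 mg QD and discontinuation.
- **(c) Strong inducer, no substitute:** replace the toxicity-monitoring instruction with Medical Monitor review of whether to continue, and record the period of co-administration.
- **(d) Section 5.2.1:** cross-reference the strong-inhibitor restriction in the prophylaxis sentence.
- **(e) Appendix G:** grade the inducers and add rifampin as strong.

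Flagging AEs with onset during strong-inhibitor use is optional. Concomitant medications are already coded under Section 10.4.3, and Section 10.4 leaves the full analysis description to the SAP.

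The cost is amendment wording, with no added visits or tests. For patients, it is an occasional interruption or, rarely, a dose reduction or discontinuation. Section 8.1 warns that as little as 7 days off drug can transiently worsen disease, which is why substitution comes first and interruption is the fallback.

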#### **5.4 Exploratory Correlatives**

Testing for circulating tumor DNA (ctDNA), lymphoma biopsies, and exploratory blood samples may be performed to evaluate MRD and lymphoma genome alterations.

Adaptive Biotechnologies will perform the MRD analysis to investigate potential changes in MRD status ( $MRD^+$  to  $MRD^-$ ) in response to acalabrutinib therapy as well as MRD correlations to bone marrow (BM) compared to whole blood as outlined in Section 6.5.12.

## **6. STUDY ASSESSMENTS AND EVALUATIONS**

### **6.1 Overview**

All patients should visit the study center on the days specified within this protocol. The complete Schedule of Assessments for this study is presented in Appendix D.

### **6.2 Baseline Study Assessments, Screening #1 Prior to BMT**

The following information will be collected and procedures will be performed for each patient at a baseline study assessment. This screening assessment will take place following written informed consent (see Section 13.3) and within 3 days prior to taking the study drug.

- Medical history and demographics
- Physical examination (including height [screening only] and weight)
- Serum or urine pregnancy test for women of child-bearing potential (WoCBP)
- Archival lymphoma sample collection

### **6.3 Baseline Study Assessments, Screening #2 Post-BMT – Day 80 to Day 100**

- Physical examination (including weight)
- ECOG performance status
- Vital signs (pulse, blood pressure, oxygen saturation, and body temperature)
- 12-lead electrocardiogram (ECG)
- Complete blood count (CBC), clinical chemistry panel, and coagulation testing
- Urinalysis
- Serum or urine pregnancy test for WoCBP
- Screening for HIV, Hepatitis B (HBV) and Hepatitis C (HCV) viruses (see Section 3.3 [exclusion criteria #7 and #17])
- Archival lymphoma biopsy collection, if not collected during Screening #1
- Blood sample collection and bone marrow aspirate for MRD analysis
- Computed tomography (CT)/ magnetic resonance imaging (MRI)/ positron emission tomography (PET) scans
- Concomitant medication review and AE evaluation

### **6.4 Study Assessment Timing**

The maintenance treatment period begins on the day the patient receives the first administration of acalabrutinib (Day 100). Dates for study visits and assessments will be determined based upon the first day after the BMT and should occur based on the timing parameters outlined in this protocol.

#### **6.4.1 Cycle 1, Days 1 and 15 (~4 months post-BMT)**

- Physical examination and vital signs (including weight)
- ECOG performance status
- CBC and clinical chemistry panel
- Concomitant medication review and AE monitoring
- Treatment with acalabrutinib 129 mg PO BID

#### **6.4.2 Cycles 2-6, Day 1 (~5-9 months post-BMT)**

- Physical examination and vital signs (including weight)
- ECOG performance status
- CBC and clinical chemistry panel
- Screening for viruses (see Section 6.5.6)
- Blood sample collection for MRD analysis
- CT/MRI/PET scans (6 months post-BMT)
- Treatment with acalabrutinib 129 mg PO BID
- Concomitant medication review and AE monitoring

